5.5 RANDOMISATION

5.5.1 Randomisation Procedures

The electronic randomisation system and trial database are hosted by the University of Nottingham. Randomisation involves minimisation on key prognostic factors including: age, sex, stroke severity (NIHSS), dependency resulting from the stroke, systolic blood pressure $\leq/ > 140$, smoker status, time after stroke, years of education. Years of education give an estimate of pre-morbid cognitive ability and predicts post-stroke cognitive impairment; BP and smoking predict recurrent stroke; delay since stroke reflects disease activity; age, sex and stroke severity are standard minimisation variables. This approach ensures concealment of allocation (note allocation concealment means that it is not possible to guess which treatment the next patient will be randomised to), minimises differences in key baseline prognostic variables, and improves statistical power. Randomisation will not be minimised by Centre because this may result in high rates of allocation prediction, but a pre-specified post-hoc analysis by centre will be performed to investigate and adjust for heterogeneity of treatment effect by centre.

Randomisation will allocate a trial treatment, which will be prepared by the local participating Pharmacy.

Note that randomisation will be performed during normal office hours (09.00 – 17.00) and the trial allows for randomisation to occur months or years after the stroke. Therefore, in the event of computer failure (for example: server failure), the investigator will wait until the computer system is re-established to perform the randomisation. Normally, this would only be a few minutes to two hours. However, if this delay requires the patient to return on a separate occasion to collect the drugs, then a separate appointment will be made and the patient's travel expenses covered as per other trial visits.

Patients will be randomised to one of the following at a 1:1 ratio as per Section 6.2:

- cilostazol versus no cilostazol
- isosorbide mononitrate versus no isosorbide mononitrate

resulting in a partial factorial comparison of cilostazol versus isosorbide mononitrate versus both drugs versus neither drug.

The randomisation algorithm will allocate a unique identifier which will be used to label the treatment pack containing the appropriate drug made up for the patient and dispensed by the local Pharmacy.

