9 STATISTICS AND DATA ANALYSIS

9.1 SAMPLE SIZE CALCULATION

There are few data on which to base sample size. There is little experience with cilostazol in Europe or North America, and little experience with ISMN in this group of patients in the UK (or in any patients with stroke). We have been guided by colleagues in Japan where cilostazol is in common use and there is experience with it in stroke. The main purposes of the trial are to assess tolerability and safety.

Table 6 Annual absolute risks (%) of outcome events after lacunar stroke

Vascular death	Non-vasc death	Non-fatal isch stroke or TIA	Non-fatal ICH	MI	MACE	Dependent (mRS 3-5)	Any cogn impt.	Dementia
1.8	0.5	2.5	0.5	0.6	3	15	30	15

We calculated mean annual event rates (Table 6) from trials (SPS3,³³ lacunar patients in ENOS⁵⁰ IST-3,⁶³ of cilostazol, Figure 1) and observational data (LADIS;⁶⁴ our^{4, 65} and other⁶⁶

studies). We expect deaths including vascular deaths of median 2.0% p.a., with 4% being the upper 95% CI of 2% in 400 patients.³³ LACI-2 therefore has a sample size of 400.

For a main Phase III trial, recurrent stroke 2.5%pa, MI 0.6%pa and vascular death 1.8%pa,^{4, 33} (MACE) are infrequent; new cognitive impairment c16% at one year,^{6, 66} dependency 15%, are frequent and important to patients, justifying their inclusion in a composite primary outcome. However, these event rates are imprecise with wide ranges; more precise estimates are needed. We estimate main Phase III trial sample size at 1100 (Table 7), assuming 80% power, alpha 5%, 10% loss to follow-up, composite event rate (45%) and conservative estimate of cilostazol effect (20% RRR is the lower 95% CI of effect, Figure 1). A primary outcome including MRI SVD progression (A, below) was considered but at least 15% of patients miss repeat MRI, sample sizes were similar (or larger, due to variance in WMH change⁶⁵ short term), the cost is much higher and the WMH intermediary measure is less relevant to patients.

Table 7. Sample size for composite outcome in main trial, estimated event rates.

Composite model	A	B	Ci	Cii	D
Composite outcome for Phase III includes:	MACE, dementia, non-vasc death, new MR signs	MACE, dementia, death	MACE, cog↓, dependency↓, death		MACE, cog imp, depend, all death
1-beta (power)	80%	80%	80%	80%	80%
Event rate, control, pa	50%	10%	30%	30%	45%
Relative risk reduction	20%	20%	20%	30%	20%
Event rate, active, pa	40%	8%	24%	21%	36%
Total sample size	950	6626	1784	778	976

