8b Secondary Objectives: To assess drug tolerability, safety, recruitment rates and accuracy, outcome event rates and retention in preparation to a large phase III randomised controlled trial to prevent recurrent lacunar stroke and physical and cognitive impairment.

This SAP focuses on these primary and secondary objectives. Planned follow-on publications will address tertiary questions.

SECTION 3. STUDY METHODS

9 Trial design

Prospective randomised open-label blinded end-point (PROBE) partial-factorial phase IIb/c trial aiming to recruit 400 patients recruited in UK Stroke Network Centres, with follow-up to one year.

10 Randomisation: By central computer-generated allocation at the University of Nottingham with minimisation on key prognostic factors: age, sex, stroke severity (NIHSS), dependency resulting from the stroke, systolic blood pressure $\leq/ > 140$ mmHg, smoking status, time after stroke, and years of education.

11 Sample size/power considerations

Conservatively, we have used sample size calculations based on binary measures. Use of ordinal measures at the time of analysis will increase statistical power.

11a Event rates: Annual event rates (Table A) were assessed from trials (SPS3,⁵ lacunar patients in ENOS,^{6 7} IST-3^{8 9}) and observational data (LADIS;¹⁰ our¹¹⁻¹³ and other¹⁴ studies). All-cause death rates were assumed to be 2.0% with upper 95% CI of 4% in 400 patients.⁵ Hence, the sample size was set at 400 participants.

Table A Annual absolute risks (%) of outcome events after lacunar stroke

Vascular death	Non-vascular death	Non-fatal IS or TIA	Non-fatal ICH	MI	MACE	Dependent (mRS 3-5)	Cognitive impairment	Dementia
1.8	0.5	2.5	0.5	0.6	3	15	30	15

ICH: intracerebral haemorrhage; IS: ischaemic stroke; MACE: major adverse cardiac events; MI: myocardial infarction; mRS: modified Rankin scale; TIA: transient ischaemic stroke

11b Comparison of two groups in a future phase III trial: Assuming power 0.80, alpha=0.05, 1:1 randomisation, composite event rate (MACE, dementia, non-vascular death, new MRI signs) 45% and absolute reduction 9% (relative risk reduction 20%), and loss to follow-up 10%, a sample size of 1100 will be needed. A

number of outcomes are relevant to patients with SVD and using these has implications for the sample size (Table B).

Table B. Sample size for composite outcome in main trial using estimated event rates.¹

Composite model	A	B	Ci	Cil	D

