- Death, including fatal haemorrhage, aiming for less than outside the upper 95% CI of 2% per year.
- The *combined rate* of recurrent stroke, MI, death, cognitive impairment and dependency, aiming for 40-50% at one year after enrolment.

Comparison of rates of events between the treatment groups: cilostazol vs no cilostazol, ISMN vs no ISMN, and cilostazol and ISMN vs neither, for:

- Systemic or intracranial bleeding, recurrent cerebral and systemic vascular events, and vascular and non-vascular causes of death.
- Death, all cause.
- New ischaemic or haemorrhagic stroke lesion or increase in SVD lesions on MRI.
- Composite of: recurrent clinically-evident stroke, MI, death, cognitive impairment (including dementia) and dependency.
- Individual event: stroke (clinically-evident or imaging-detected ischaemic or haemorrhagic stroke to be reported separately), TIA, myocardial ischaemia, cognitive impairment and dementia.
- New infarcts and haemorrhages, absolute and change in WMH, microhaemorrhages, lacunes, atrophy imaging variables from central read of baseline imaging and one year MRI
- The comparisons of combined cilostazol and ISMN versus neither, whilst being very underpowered statistically, are presented since these may be the two groups studied in the planned follow-on trial.

Central tendency, comparisons and regressions will be analysed as follows (**Table D**).

Table D. Descriptive and analytical statistics

	Binary	Nominal	Ordinal	Continuous
Central tendency and distribution	N (%)	N (%)	Median [interquartile range]	Mean (standard deviation)
Comparisons	Chi-square (2x2)	Chi-square (2x2, or rxc)	Mann-Whitney U or Kruskal-Wallis	t-test (pooled) or 1-way ANOVA
Regression	Binary logistic regression (BLR)	-	Ordinal logistic regression (OLR)	Multiple linear regression (MLR)

27b Covariate adjustment: Analyses will be adjusted for minimisation covariates:

- Age, sex, stroke severity (NIHSS), dependency resulting from the stroke, systolic blood pressure, smoking status, time after stroke, years of education.

Covariate adjustment with continuous variables (age, NIHSS, SBP, time after stroke, years of education) will use original, not dichotomised, data.

27c Assumption checking: The assumption of proportionality will be tested using the likelihood test.

27d Alternative methods: If the data fail the assumption of proportionality (tested using the likelihood test), we will use alternative methods such as multiple logistic regression.

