Table 7a. Participants with at least one serious adverse events by organ randomised to isosorbide mononitrate (ISMN) versus none.

Data are number (%); comparison by binary logistic regression.

Number	ISMN	All No ISMN		ISMN	Fatal No ISMN		Difference (p)
		ISMN	Difference (p)		ISMN	Difference (p)	
Cardiovascular	xx (xx.x)	xx (xx.x)	(xx.x, xx.x), p=0.xxx	xx (xx.x)	xx (xx.x)	(xx.x, xx.x), p=0.xxx	
Myocardial infarction	xx (xx.x)	xx (xx.x)	(xx.x, xx.x), p=0.xxx	xx (xx.x)	xx (xx.x)	(xx.x, xx.x), p=0.xxx	
Nervous system	xx (xx.x)	xx (xx.x)	(xx.x, xx.x), p=0.xxx	xx (xx.x)	xx (xx.x)	(xx.x, xx.x), p=0.xxx	
Ischaemic stroke	xx (xx.x)	xx (xx.x)	(xx.x, xx.x), p=0.xxx	xx (xx.x)	xx (xx.x)	(xx.x, xx.x), p=0.xxx	
Transient ischaemic attack	xx (xx.x)	xx (xx.x)	(xx.x, xx.x), p=0.xxx	xx (xx.x)	xx (xx.x)	(xx.x, xx.x), p=0.xxx	
Intracerebral haemorrhage	xx (xx.x)	xx (xx.x)	(xx.x, xx.x), p=0.xxx	xx (xx.x)	xx (xx.x)	(xx.x, xx.x), p=0.xxx	
Respiratory	xx (xx.x)	xx (xx.x)	(xx.x, xx.x), p=0.xxx	xx (xx.x)	xx (xx.x)	(xx.x, xx.x), p=0.xxx	
Gastrointestinal	xx (xx.x)	xx (xx.x)	(xx.x, xx.x), p=0.xxx	xx (xx.x)	xx (xx.x)	(xx.x, xx.x), p=0.xxx	
Genitourinary	xx (xx.x)	xx (xx.x)	(xx.x, xx.x), p=0.xxx	xx (xx.x)	xx (xx.x)	(xx.x, xx.x), p=0.xxx	
Secondary	xx (xx.x)	xx (xx.x)	(xx.x, xx.x), p=0.xxx	xx (xx.x)	xx (xx.x)	(xx.x, xx.x), p=0.xxx	
Haematological	xx (xx.x)	xx (xx.x)	(xx.x, xx.x), p=0.xxx	xx (xx.x)	xx (xx.x)	(xx.x, xx.x), p=0.xxx	
Metabolic/endocrine	xx (xx.x)	xx (xx.x)	(xx.x, xx.x), p=0.xxx	xx (xx.x)	xx (xx.x)	(xx.x, xx.x), p=0.xxx	
Musculoskeletal	xx (xx.x)	xx (xx.x)	(xx.x, xx.x), p=0.xxx	xx (xx.x)	xx (xx.x)	(xx.x, xx.x), p=0.xxx	
Infection/sepsis	xx (xx.x)	xx (xx.x)	(xx.x, xx.x), p=0.xxx	xx (xx.x)	xx (xx.x)	(xx.x, xx.x), p=0.xxx	
Tumour/malignancy	xx (xx.x)	xx (xx.x)	(xx.x, xx.x), p=0.xxx	xx (xx.x)	xx (xx.x)	(xx.x, xx.x), p=0.xxx	
Other	xx (xx.x)	xx (xx.x)	(xx.x, xx.x), p=0.xxx	xx (xx.x)	xx (xx.x)	(xx.x, xx.x), p=0.xxx	
Total	xx (xx.x)	xx (xx.x)	(xx.x, xx.x), p=0.xxx	xx (xx.x)	xx (xx.x)	(xx.x, xx.x), p=0.xxx	

Table 7b. Participants with at least one serious adverse events by organ randomised to cilostazol (Cil) versus none.

Data are number (%); comparison by binary logistic regression.

Number	All			Fatal		
	Cil	No Cil	Difference (p)	Cil	No Cil	Difference (p)
Cardiovascular	xx (xx.x)	xx (xx.x)	(xx.x, xx.x), p=0.xxx	xx (xx.x)	xx (xx.x)	(xx.x, xx.x), p=0.xxx
Myocardial infarction	xx (xx.x)	xx (xx.x)	(xx.x, xx.x), p=0.xxx	xx (xx.x)	xx (xx.x)	(xx.x, xx.x), p=0.xxx

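### Fully adjusted logistic regression is planned, with no sparse-event rule, for outcomes such as MI and intracerebral haemorrhage where about two events are expected

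*SAP*

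**What the plan says.** SAP Table D lists "Binary logistic regression (BLR" as the regression method for binary data. SAP 27b adds: "Analyses will be adjusted for minimisation covariates". The eight are age, sex, NIHSS, dependency, systolic blood pressure, smoking, time after stroke and years of education. With treatment this makes 9 slopes, or 10 if smoking enters as current, past or never, as in SAP Table 1.

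SAP Table 3 applies this adjusted model to TIA, MI and death, among others. SAP Tables 7a-c apply logistic regression to every row, for all and for fatal serious adverse events (SAEs): "Data are number (%); comparison by binary logistic regression". Their caption does not repeat the covariates. Protocol 9.2 names logistic regression for SAEs, recurrent stroke and MI, and says that the safety models are adjusted for the minimisation variables.

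Neither document gives a minimum event count, a penalised or exact method, or a counts-only rule. The fall-back in SAP 27d is triggered by failure of proportionality. The unadjusted analysis in SAP 27e is for the primary outcome, which is recruitment and retention.

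**The concern.** A logistic model needs events in both arms before the treatment odds ratio can be estimated, and it needs several events per fitted slope before the estimate is stable. The plan's own event rates suggest that some outcomes fail the first condition more often than not, and that others fail the second.

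Protocol 9.1 names tolerability and safety as the trial's main purposes, and SAP 27a lists bleeding, vascular events and death among the between-group comparisons. If a model does not converge, or returns an extreme odds ratio, someone must choose a replacement. SAP 13a has provisional data analysed at a soft lock, so without a rule that choice would follow sight of which models failed. A SAP is meant to remove that discretion.

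**Working it through.** **Inputs**
- SAP Table A, annual rates in per cent (vascular death, non-vascular death, ischaemic stroke or TIA, non-fatal ICH, MI, MACE, dependency, cognitive impairment, dementia): "1.8 0.5 2.5 0.5 0.6 3 15 30 15". Protocol 9.1 agrees for two of these: "MI 0.6%pa and vascular death 1.8%pa".
- Size: "Hence, the sample size was set at 400 participants" (SAP 11a); SAP Table 2 records 363 recruited.
- Duration: "with follow-up to one year" (SAP 9), so expected events = N × rate.
- Allocation: "Patients will be randomised to one of the following at a 1:1 ratio" (Protocol 5.5.1). A single-drug comparison has about 363/2 = 181.5 per arm; both drugs versus neither has about 363/4 = 90.75 per arm.

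**The plan's own figure.** SAP 11a puts the upper 95% limit for 2.0% in 400 at 4%. With 8/400, the exact and Wilson limits are both 3.9%, so the figure reproduces. The plan states no expected count for MI, ICH or SAEs.

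**Expected events in 363 patients**
- MI: 363 × 0.006 = 2.2, or 0.22 to 0.24 per slope (10 or 9 slopes).
- Non-fatal ICH: 363 × 0.005 = 1.8, or 0.18 to 0.20 per slope.
- All deaths: 363 × 0.020 = 7.3 at the SAP 11a rate; 363 × (0.018 + 0.005) = 8.3 from Table A. Per slope, 0.73 to 0.92.
- Ischaemic stroke or TIA: 363 × 0.025 = 9.1, about 0.9 to 1.0 per slope.
- Dependency and dementia: 363 × 0.15 = 54 each. Cognitive impairment: 363 × 0.30 = 109.

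**Chance that at least one arm has no events.** With the same rate r in both arms and n per arm, q = (1 − r)^n and P = 2q − q².

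| Outcome | Comparison | q | P |
|---|---|---|---|
| MI | single drug | 0.994^181.5 = 0.336 | 56% |
| ICH | single drug | 0.995^181.5 = 0.403 | 64% |
| MI | both v neither | 0.994^90.75 = 0.579 | 82% |
| ICH | both v neither | 0.995^90.75 = 0.634 | 87% |

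At the planned 400 the four figures are 51%, 60%, 80% and 84%.

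**Range.** Protocol 9.1 calls the rates imprecise. Assuming half or double the rate, the single-drug figure becomes 82% or 21% for MI, and 87% or 30% for ICH.

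**Adjusted model.** A simulation (300 runs per case; independent covariates with no true effects, both assumed) fitted treatment plus all eight covariates. In 363 patients there were no events, or no finite maximum-likelihood solution for the full model, in 93% of runs for MI and 96% for ICH. For death and ischaemic stroke or TIA the share was 29% to 38%; where the model did fit, the upper 95% limit was typically 16 to 21 times the lower. The zero-arm figures above need no covariate assumption and are the firmer result.

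**SAE tables.** Each of Tables 7a-c has 17 rows × 2 = 34 comparisons. The 7 to 8 deaths supply all 17 fatal comparisons. Adding MI, ischaemic stroke, TIA and ICH among all SAEs, 17 + 4 = 21 of 34 expect roughly ten events or fewer.

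**The case against.** **Another method is already written.** Table D lists chi-square for binary comparisons, Tables 4 and 6a-c use it, and Table 2 gives counts only. That stands: the SAP is incomplete here, not silent. But with 2.2 or 1.8 events the expected event cells are about 1.1 and 0.9 per arm, where chi-square is unreliable, and Tables 3 and 7 still call for regression.

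**Adjustment in Table 7 is inferred.** True: it follows from SAP 27b and Protocol 9.2. Dropping the covariates would not help an outcome with an empty arm.

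**No main conclusion depends on these odds ratios.** The primary endpoint is recruitment and retention, death is tabulated against 2%, SAP 26a puts myocardial ischaemia under efficacy, and every row shows counts. This stands and limits the stakes. The safety data stay visible; what fails is the planned comparison.

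**The rates are rough.** Also true, hence the range. The ICH rate covers non-fatal events only, whereas the Table 7 row for all ICH is not so limited.

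**What a reader might wrongly infer.** It is tempting to say that most SAE rows will fail, or that every binary outcome is affected. Table A gives no rate for non-fatal respiratory, gastrointestinal, infection or other organ-class SAEs, so those rows cannot be judged. Protocol 10.3.2 and 10.3.3 may thin them, but no count follows. Dependency, dementia and cognitive impairment are not sparse in the single-drug comparisons.

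**Conclusion.** The concern holds for a defined set of outcomes. For MI and non-fatal ICH the planned treatment odds ratio has no finite non-zero estimate in about 56% and 64% of single-drug comparisons, and in about 82% and 87% of comparisons of both drugs with neither. All deaths and ischaemic stroke or TIA can usually be estimated in the single-drug comparisons, but not stably with nine or ten slopes. The fatal columns of Tables 7a-c share seven to eight deaths and are weaker still.

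This rests on Table A rates, equal rates in the two arms, equal allocation, 363 patients and one year of follow-up. Complete-case analysis (SAP 20) and patients randomised for one drug only would lower the counts.

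SAP 27a concedes that the comparison of both drugs with neither has very little power. That is a different matter from whether an estimate exists. A rule for sparse outcomes should be added; the feasibility conclusions are not affected.

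**What to change.** Add to SAP 27a a rule based on total events in the comparison, fixed before any unblinded analysis, including the one at soft lock:
- **Fewer than 5 events:** counts and the risk difference with an exact 95% CI; no model and no p-value.
- **5 to about 20 events:** Firth-penalised logistic regression with treatment and at most one or two minimisation covariates named in advance, alongside the unadjusted risk difference with a score-based 95% CI.
- **More events:** the planned fully adjusted model, including for dependency, dementia, cognitive impairment and the composite.

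The cut-offs are judgement; the documents give none. A trigger of ten events per parameter would be too wide: with ten parameters it needs 100 events and would strip covariates from dependency and dementia (54 each). Under the rule proposed here, those two keep full adjustment even for both drugs versus neither, where 181 × 0.15 = 27 events are expected, about 2.7 per slope. Those estimates should be read with care.

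The cost is one paragraph of SAP text and standard options in SAS 9.4, the software named in SAP 31. The downside is less covariate adjustment for the rare outcomes only.
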